| PM+ | Problem Management Plus |
| PHQ-9 | Patient Health Questionnaire for depression scoring each of the 9 DSM-5 criteria |
| PHQ-ADS | Patient Health Questionnaire – Anxiety and Depression (sum score of PHQ-9 and GAD-7) |
| PTSD | Posttraumatic Stress Disorder |
| RESPOND | pREparednesS of health systems to reduce mental health and Psychosocial concerns resulting from the COVID-19 paNDemic |
| RCT | Randomized Controlled Trial |
| WHO | World Health Organization |

2. SUMMARY

Rationale: The ongoing COVID-19 pandemic has a major and potentially long-lasting effect on mental health and wellbeing across populations worldwide. Vulnerable groups, such as asylum seekers, refugees and migrants, are disproportionately affected by the COVID-19 pandemic. There is a high need for psychosocial interventions that can target the most prevalent mental health problems as a result of the COVID-19 pandemic, addressing the needs of many people in a way that maximizes the use of resources. The World Health Organization (WHO) has developed two scalable, low-intensity psychological interventions: Doing What Matters in times of stress (DWM; a self-help intervention) and Problem Management Plus (PM+; a face-to-face intervention). DWM and PM+ can be delivered by paraprofessionals, are applicable to a variety of mental health problems (depression, anxiety and PTSD), and can be adapted to different populations, cultures and languages. Both DWM and PM+ have been proven to be effective on their own. In this study, DWM and PM+ will be combined into a stepped-care intervention. This study is part of the larger EU H2020-RESPOND project, which aims to improve the preparedness of the European mental health care system in the face of future pandemics.

Objective: The main objective is to evaluate the implementation and (cost-)effectiveness of the culturally and contextually adapted DWM/PM+ stepped-care programs amongst asylum seekers, refugees, and/or migrants living in Italy during the COVID-19 pandemic in terms of mental health outcomes, resilience, wellbeing, health inequalities, and costs to health systems. The main hypothesis is that the stepped-care DWM/PM+ intervention together with psychological first aid (PFA) in addition to care-as-usual (CAU) will be more effective in decreasing psychological distress and symptoms of mental health problems than PFA and CAU alone. We aim to conduct a randomized controlled trial (RCT) to assess the (cost-)effectiveness of the stepped-care DWM/PM+ intervention, and to identify (a) barriers and facilitators to treatment engagement and adherence and (b) opportunities for scaling up the implementation of the DWM/PM+ intervention within the existing health care system in Italy.

Study design: pragmatic implementation trial with a single-blinded, randomized, parallel-group design. The final phase of the trial will consist of a qualitative process evaluation with individual interviews and focus group discussions (FGDs). The qualitative phase will include some participants in the randomized trial who completed DWM ($n=2/4$), who completed PM+ ($n=2/4$), who dropped-out during DWM ($n=2/4$), and who dropped-out during PM+ ($n=2/4$); (b) local stakeholders ($n=10/15$) (c) facilitators of the DWM and PM+ intervention (both helpers and trainers/supervisors).

Study population: Adult asylum seekers, refugees or migrants with self-reported elevated psychological distress ($K10 >15.9$) ($n=212$).

Intervention (if applicable): All participants (in both the treatment and the comparison group) will receive Psychological First Aid (PFA) and CAU. In addition to PFA and CAU, the treatment group will receive the stepped-care intervention (DWM with or without PM+). The stepped-care intervention consists of DWM (step 1), and conditionally PM+ (step 2) if participants still meet criteria for psychological distress ($K10 >15.9$) 2 weeks after having received DWM. DWM, i.e. a self-help book with pre-recorded audios, has been adapted as an online intervention (phase 1). PM+ consists of five sessions and will be delivered by trained peer-support helpers in person or via teleconferencing in individual or group format. In addition to PFA, the comparison group will receive CAU which ranges from community care to specialized psychological treatments, according to the needs and clinical characteristics of participants.

Main study parameters/endpoints: Screening for inclusion and exclusion criteria will be interviewer-administered, in-person or through (video) calls. For all participants, online assessments will take place at baseline, at 2 weeks after having received DWM, at 1 week and at 2 months after having received PM+. The primary outcome will be the decrease in symptoms of anxiety and depression from baseline to two-month follow-up, measured through the sum score of the Patient Health Questionnaire (PHQ-9) and General Anxiety Disorder-7 (GAD-7), i.e. the PHQ-Anxiety and Depression Score (PHQ-ADS). We expect to detect a Cohen's d effect size of 0.3 in the DWM/PM+ group at 2 months post-treatment. Additional health outcomes include level of anxiety (GAD-7) and depression (PHQ-9), symptoms of posttraumatic stress disorder (PCL-5), resilience (Mainz Inventory of Microstressors MIMIS), quality of life (EQ-5D-5L), and cost of care (CSRI). Additional study parameters will include demographic data, COVID-19 related (exposure) variables, treatment fidelity, satisfaction and acceptability of the intervention program, and implementation indicators (such as reach, dose, resource use, intervention related costs). Through FGDs and interviews at the end of the trial, the

feasibility of scaling-up the implementation on the stepped-care DWM/PM+ intervention within asylum seekers, refugees, and migrants in Italy.

3. INTRODUCTION AND RATIONALE

Impact of pandemic and containment measures

The ongoing COVID-19 pandemic has a major and potentially long-lasting effect on mental health and wellbeing across populations in Europe and worldwide. The pandemic has affected every country in the world, with some of the most deeply affected countries in Europe, including Italy (John Hopkins University and Medicine, 2020). Early reports regarding the levels of psychological distress associated with the COVID-19 crisis are highly concerning (McGinty, Presskreischer, Han & Barry, 2020) and led to the UN releasing a policy briefing on the mental health impacts of COVID-19 warning that a 'long-term upsurge in the number and severity of mental health problems is likely' (United Nations, 2020).

European governments installed epidemic control measures to contain the spreading of the virus, which include lockdown restrictions and closures (amongst others) that have created a great impact on society (Blavantnik School of Government, University of Oxford, 2020). Physical distancing and staying at home orders have led to elevated loneliness in many people, which is in turn associated with depression and suicidal ideation (Stickley & Koyanagi, 2016). Despite social protection programs, many individuals have directly been impacted financially by the economic consequences of the containment measures, and have seen their income decline, especially people with short-term or part-time contracts, or those being self-employed. Economic estimates show that the lockdown will directly affect sectors amounting to up to a loss of 2 percentage points in annual GDP growth for each month of containment (OECD, 2020). Following economic recession, mental health problems have been shown to increase (Garcy & Vagero, 2013).

Focus on vulnerable groups

Although the COVID-19 pandemic has affected the whole population, consequences are not distributed equally. COVID-19 has had a larger effect on people living under fragile circumstances, and on socio-economically disadvantaged and minority populations across Europe. The risk of dying from COVID-19 is higher among people in socio-economically deprived areas than among people in the least deprived areas (Public Health England, 2020). Furthermore, historically, following recession higher increases in mental health symptoms of younger working-age people have been found (Thomson & Katikireddi, 2018). Thus, the COVID-19 pandemic and the associated containment measures are expected to lead to an exacerbation of health inequalities in Europe and beyond. In May 2020, the WHO already stated that particular attention should be given to vulnerable groups, including asylum seekers, refugees, and migrants (ARM)(WHO, 2020b).

ARM resettled in high-income countries are exposed to multiple health-related risks and vulnerabilities than the general population, due to their exposure to complex traumatic events before and during transition, and to additional traumatic events once resettled in a hosting country (Turrini et al, 2017). In particular, in the COVID-19 pandemic ARM may lack biosecurity measures as basic protection equipment due to insufficient information. They are also at high risk of infection because of proximity, lack of sanitation, and poor living conditions. There is evidence of discrimination and social exclusion amongst resettled ARM living in areas associated with COVID-19 (IASC, 2019; WHO, 2020). These reports are in line with previous evidence indicating that discrimination has been a key concern even in the general population in relation to other viral outbreaks and epidemics (Person et al, 20014). In addition, asylum seekers, refugees, and migrants are often left out of disaster preparedness planning, and may experience lack of access to information delivered in a culturally appropriate way, with problems in adapting their behaviors to protection measures and social rules such as social distancing.

The Box 1 below reports the definitions of asylum seekers, refugees, and migrants (ARM) according to the UNHCR (UNHCR, 2018).

| | |
|-----------------------|---|
| Asylum seekers | Asylum seekers are persons fleeing armed conflict or persecution, but whose request for sanctuary has yet to be processed. |
| Refugees | Refugees are persons fleeing armed conflict or persecution. Their situation is often so perilous and intolerable that they cross national borders to seek safety in nearby countries, and thus become internationally recognized as "refugees" with access to assistance from States, UNHCR, and other organizations. They are so recognized precisely because it is too dangerous for them |

| | |
|-------------------------------|--|
| | to return home, and they need sanctuary elsewhere. These are people for whom denial of asylum has potentially deadly consequences. |
| Migrants (economic) | Migrants choose to move not because of a direct threat of persecution or death, but mainly to improve their lives by finding work, or in some cases for education, family reunion, or other reasons. Unlike refugees who cannot safely return home, migrants face no such impediment to return. If they choose to return home, they will continue to receive the protection of their government. |

Scalable psychological interventions to improve resilience, mental health and wellbeing

There is a high need of psychosocial interventions for at-risk groups, such as ARM, affected by traumatic events and additionally by the COVID-19 pandemic to address the most prevalent mental health problems, most notably symptoms of distress, anxiety, depression, and posttraumatic stress disorder (PTSD). Telehealth has proven to be effective for delivery of individual or group-based mental health and psychosocial support interventions (Banbury, Nancarrow, Dart, Gray & Parkinson, 2018), and has great advantages over regular mental health care delivery in terms of its feasibility under lockdown restrictions, scalability, and reducing costs. This can be particularly useful for ARM resettled in Italy who experience various barriers to (mental) health care. However, it is yet unclear whether it has met the needs of more vulnerable people with specific needs, who are illiterate, older, or people without internet access (EuroHealthNet, 2020).

The World Health Organization (WHO) has developed a number of scalable psychological interventions for populations affected by adversity (WHO, 2017). They include -amongst others- Doing What Matters in Times of Stress (DWM) and Problem Management Plus (PM+). A core feature of all WHO scalable interventions is that they can be trained to and delivered by non-professional helpers, such as a trained peer, or helper at the workplace, or a psychosocial worker (task-shifting) (WHO, 2017; Epping-Jordan et al., 2016). They have also been designed to be widely applicable to a variety of mental health problems (depression, anxiety and PTSD) and easily adaptable to different populations, cultures and languages. Finally, the interventions and their implementation materials are freely available on the WHO website.

DWM was originally designed for flexible implementation either in a group or individual format including an online format. People participating in DWM also receive support from a briefly trained helper. DWM is based on acceptance and commitment therapy (ACT), a modern form of cognitive-behavioral therapy with a strong focus on mindfulness practices and includes exercises which aim to enhance stress reduction and build social support, adaptive coping and resilience (Epping-Jordan et al., 2016). It has been implemented with different populations of asylum seekers and refugees in Europe, Turkey (Purgato et al., 2019) and Northern Uganda (Tol et al., 2020). In RESPOND, the DWM pre-recorded audios and an illustrated stress management guide called "Doing What Matters in Times of Stress: an illustrated guide" (WHO, 2020a), has been culturally adapted to an online application tool. This way, people can use the self-help intervention in their own time. The five weekly sessions of the intervention will follow the five chapters of the book (grounding, unhooking, acting on your values, being kind and making room). Participants will receive a weekly call from a so-called "helper" to support them accessing the intervention sessions, and to shortly revise the contents of each session.

PM+ is a transdiagnostic intervention (Banbury et al., 2018) for reducing symptoms of depression, anxiety, PTSD, and related conditions, is delivered by trained non-specialized workers or lay people, and is available in individual and group delivery formats for face-to-face or online delivery. PM+ comprises five weekly sessions using evidence-based techniques: of (a) problem solving, (b) stress management, (c) behavioral activation, and (d) accessing social support. PM+ has been successfully implemented in Kenya (Bryant et al., 2017) and Pakistan (Rahman et al., 2016b). Both DWM and PM+ have been implemented through two large EU H2020 funded projects, STRENGTHS (733337) and RE-DEFINE (779255). For this study, we adapted both the DWM and the PM+ intervention to the COVID-19 pandemic and to the context and culture of the target population, i.e. we adapted examples and pictures used in the intervention.

RESPOND Project

This study is embedded in the larger, EU H2020 CORONAVIRUS-funded RESPOND (PREparednesS of health systems to reduce mental health and Psychosocial concerns resulting from the COVID-19 paNDemic) project. The RESPOND project

aims to improve the preparedness of the European mental health care system in the face of future pandemics. In order to do that a consortium of eight countries (BE, DE, ES, FR, NL, IT, SWE, UK) will collaborate in:

- 1) Identifying risk groups for poor wellbeing and mental health related to the COVID-19 pandemic by analyzing longitudinal epidemiological data and identifying resilience factors related to the COVID-19 pandemic;
- 2) Examining the impact of the COVID-19 pandemic on long-term health and mental health services use, and the associations between health and mental health care use and socio-economic factors across European countries with different control measures and pandemic course (Sweden, Italy and Spain);
- 3) Performing rapid and recurring holistic assessments of policies and measures across Europe that have and will address different phases of the COVID-19 pandemic to protect the mental health and wellbeing of groups at high-risk for COVID-19 related mental health issues
- 4) Examining the necessary health system and wider contextual and policy conditions for successful implementation and scaling-up of remote-delivered stepped-care using existing, scalable World Health Organization (WHO) programs to improve resilience, wellbeing, overall functioning and mental health, across frontline workers and other high-risk groups for COVID-19 related poor mental health, including ARM.
- 5) Providing regional and national health care authorities, including relevant public health and long-term care authorities, with transferable evidence-based practices, methodologies and guidance for scaling up mental health and broader social and economic support measures for frontline workers and other risk groups for COVID-19 related mental health symptoms, including ARM.

This study(-protocol) contributes to aim number 4; examining the feasibility and cost-effectiveness of remote-delivered scalable interventions for targeting COVID-19-related psychological distress and mental health issues. Both DWM and PM+ have been found to be effective (Purgato et al., 2019; Tol et al., 2020; Bryant et al., 2017; Rahman et al., 2016b), but it is unknown if they are also effective when combined as a stepped-care program compared to care-as-usual. Within Italy, the targeted vulnerable group to examine the effectiveness of the stepped-care intervention, will be asylum seekers, refugees, and migrants. The treatment group will be compared to an enhanced care-as-usual (CAU) group in terms of a number of health and implementation outcome variables.

4. OBJECTIVES

4.1. PRIMARY OBJECTIVE

To evaluate the (cost-)effectiveness, feasibility, and acceptability of the culturally and contextually adapted DWM/PM+ stepped-care program among ARM resettled in Italy during the COVID-19 pandemic in terms of mental health outcomes, resilience, wellbeing, health inequalities, and costs to health systems.

4.2. SECONDARY OBJECTIVE

To identify barriers and facilitators to treatment engagement and adherence and opportunities for scaling up among the target population in Italy (qualitative part of the study).

5. STUDY DESIGN

The study consists of a single-blind randomized controlled trial (RCT), that will include a qualitative analysis in its final phase. As a preliminary work, we conducted a qualitative study to assess the needs of ARM resettled in Italy and to inform the adaptation of the DWM/PM+ interventions. The preliminary phase has been completed and was described in a separate protocol for which ethical approval was granted by the Comitato di Approvazione della Ricerca sulla Persona – CARP – of the University of Verona.

Randomized controlled trial (stepped-care DWM/PM+ intervention with Psychological First Aid and care-as-usual vs. Psychological First Aid and care-as-usual alone).

The final phase of the RCT will include a process evaluation with qualitative interviews and focus groups to assess barriers and facilitators of engagement and adherence to the stepped-care intervention and opportunities for scaling up the implementation of the intervention.

Box 2. Summary of the present research.

Randomized controlled trial: the DWM/PM+ programs will be evaluated in a RCT. Participants will be screened for elevated distress (K10; see Figure 1). We will conduct a RCT in ARM with increased psychological distress to determine whether the stepped care intervention (i.e. DWM/PM+) leads to stronger decreases in mental health outcomes, and increase in wellbeing among compared to care-as-usual (CAU). This phase is designed as a randomized, single-blind parallel-group trial with one treatment group (n=105) and one comparison group (n=105). All participants in both the treatment and the comparison group will receive Psychological First Aid (PFA) and CAU. In addition to PFA and CAU, participants randomized into the treatment group will receive the DWM/PM+ stepped-care intervention, while participants randomized in the comparison group will receive PFA and CAU only.

All participants in the treatment group (i.e. those who receive DWM and PM+ and those who only receive DWM because symptoms subside) will be followed for a period of 2 months after the end of the PM+ session (see Figure 1 for assessment points).

The final part of the RCT will include a qualitative study, consisting of interviews and/or focus group discussions among key stakeholders (identified as reported below) to evaluate barriers and facilitators to treatment engagement and adherence to the DWM/PM+ stepped-care intervention, as well as opportunities for scaling up the implementation of the intervention within the existing healthcare system in Italy. This will inform partners in RESPOND of the synthesis and dissemination of the DWM/PM+ stepped-care intervention for vulnerable groups during a pandemic.

The qualitative study will include the following key stakeholders (a) participants in the RCT who completed DWM (n=2/4; improved and not improved), who completed PM+ (n=2/4; improved and not improved), who dropped-out during DWM (n=2/4), and who dropped-out during PM+ (n=2/4); (b) local stakeholders (n=10/15); (c) facilitators of the DWM and PM+ intervention (both helpers and trainers/supervisors).

[figure not shown]

Figure 1. Flowchart of randomized controlled trial

6. STUDY POPULATION

6.1. POPULATION

Participants for the RCT will be ARM resettled in Italy. Participants will be recruited through (a) targeted social media recruitment, (b) key stakeholders as NGOs located in Italy, and (c) other community-based organizations offering legal and/or social and/or psychosocial support for this vulnerable group.

Participants for the qualitative process evaluation will be key informants, such as participants who took part in the RCT; DWM/PM+ facilitators (helpers and supervisors); local stakeholders (recruited through participating centers in the RCT phase). For participants who took part in the RCT, we aim to include both those who took part only in DWM and those who took part in PM+ as well. Also drop-outs from both the DWM and PM+ intervention will be asked to participate in the qualitative process evaluation.

6.2. INCLUSION CRITERIA

Participants will be eligible to participate in the study if they meet all of the following criteria:

- 18 years or older;
- Living in Italy as asylum seeker, refugee, or migrant
- Having elevated levels of psychological distress (Kessler Psychological Distress Scale (K10) >15.9).
- Sufficient mastery (written and spoken) of one of the languages the DWM/PM+ intervention is being delivered in (e.g. English, Italian).
- Oral and written informed consent before entering the study.

6.3. EXCLUSION CRITERIA

Potential participants who meet the inclusion criteria will be excluded from participation in this study if they meet any of the following criteria:

- Planning to permanently move back to their home country before the last quantitative assessment at 2 months after PM+;
- Having acute medical conditions (requiring hospitalization);
- Imminent suicide risk, or expressed acute needs or protection risks that require immediate follow-up;
- Having a severe mental disorder (e.g. psychotic disorders, substance-dependence);
- Having severe cognitive impairment (e.g. severe intellectual disability or dementia);
- Currently receiving specialized psychological treatment (e.g. EMDR, CBT);
- In case of current psychotropic medication use: being on an unstable dose for at least 2 months.

6.4. SAMPLE SIZE CALCULATION

A total number of 212 participants will be included. Based on prior studies on a PM+ intervention (Bryant et al., 2017; Rahman et al., 2016b), we aim to detect a small to medium effect size Delta (defined as the square root of the ratio of the variance of the tested effect to the comparison error variance) of 0.3 in the PM+ group at 2 months post-treatment based on the primary composite outcome PHQ-ADS (Kroenke et al., 2016; 2019). The PHQ-ADS is the combined sum score of depression and anxiety symptoms of the PHQ-9 and GAD-7, respectively and has shown good internal consistency ($\alpha = .88$ to $.92$) (Kroenke et al., 2016; 2019). A power calculation for an ANOVA repeated

measurement design with two time-periods to identify the effect of treatment at the last endpoint suggests a minimum sample size of $N=74$ per group (power=0.95, $\alpha=0.05$, two-sided, $\rho=0.9$). Taking into account 30% attrition, we aim to include a total number of 212 participants (106 in the stepped-care DWM/PM+ treatment group - with PFA and CAU - and 106 in the PFA and CAU comparison group).

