The PHQ-ADS is the sum of the PHQ-9 and GAD-7 scores (details of both instruments summarized below) and thus can range from 0 to 48, with higher scores indicating higher levels of depression and anxiety symptomatology. Two validation studies of the PHQ-ADS in trial data-sets of patients with chronic (musculoskeletal) pain and oncologic diseases have been published (Kroenke et al., 2016; Kroenke et al., 2019). Evidence shows high internal reliability (Cronbach's alpha of 0.8 to 0.9), strong convergent and construct validity, sufficient unidimensionality and evidence for sensitivity to change (i.e. differentiating between individuals classified as worse, stable, or improved by a reference measure at three months post-intervention).

Secondary outcome measures

PHQ-9: depression (PHQ-9; subscale of PHQ-ADS)

Depressive symptoms during the past two weeks will be measured using the Patient Health Questionnaire depressive module. It asks how often someone was bothered by each of the nine DSM-5 criteria and scores answers on a four-point Likert scale ranging from 0 (not at all) to 3 (nearly every day) (Kroenke, Spitzer, & Williams, 2001). In addition to the nine items, the PHQ-9 asks: "If you checked off *any* problems, how *difficult* have these problems made it for you to do your work, take care of things at home, or get along with other people?", which is to be answered with "Not difficult at all", "Somewhat difficult", "Very difficult", or "Extremely difficult". For the current study, we will examine changes in caseness in depression. We will use a cut-off score of 10, which has been found to be a valid cut-off point for diagnosis (Manea, Gilbody & McMillan, 2021).

The PHQ-9 has been translated to and is available in many languages (see <https://www.phqscreeners.com/>), amongst which are English and Italian. The PHQ-9 has been found to be a reliable and valid instrument to measure depressive severity. Furthermore, due to its brevity, PHQ-9 is a useful instrument for usage in a clinical or research setting (Kroenke et al., 2001).

GAD-7: anxiety symptoms (GAD-7; subscale of PHQ-ADS)

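### The 95% power claimed for a Cohen's d of 0.3 depends on an unsourced and implausibly high correlation of 0.9, because section 6.4's Delta of 0.3 is close to d = 0.3 only at such a value

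*Protocol*

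**What the plan says.** Section 6.4 (Sample size calculation) aims at an effect size Delta, defined as the "square root of the ratio of the variance of the tested effect to the comparison error variance) of 0.3". The design is a repeated-measures ANOVA, a "measurement design with two time-periods to identify the effect of treatment at the last endpoint", and it leads to at least 74 per group, with "power=0.95, $\alpha=0.05$, two-sided, $\rho=0.9". It continues: "Taking into account 30% attrition, we aim to include a total number of 212 participants", which is 106 per arm.

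The summary gives the same target as a Cohen's "d effect size of 0.3 in the DWM/PM+ group at 2 months post-treatment", and section 8.1.1 also names a Cohen's d of 0.3.

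The value 0.9 for rho comes without a source. The earlier PM+ trials are cited for the effect size. The scale papers are cited for internal consistency: the PHQ-ADS "has shown good internal consistency ($\alpha = .88$ to $.92" in section 6.4, and in section 8.3 (primary outcome measure) "Evidence shows high internal reliability", there with a Cronbach's alpha of 0.8 to 0.9. No test-retest correlation appears anywhere in the protocol.

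**The concern.** In a two-occasion design, rho is the correlation between a participant's baseline and T4 scores. It sets how much of the T4 variance is removed by the baseline, and therefore how large a raw difference the trial can detect. Two things make 0.9 doubtful here. First, it equals the within-occasion consistency that the protocol quotes for the scale, which leaves almost no room for participants to change rank between T1 and T4. Second, that interval contains five weeks of DWM, a two-week gap, five weekly PM+ sessions for those stepped up, and two months of follow-up.

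A reader of the summary and section 8.1.1 will take it that the trial has 95% power for a standardised difference of 0.3. If the true rho is clearly lower, that power is much smaller, and a null result could be read as good evidence of no effect when it is not.

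**Working it through.** **Inputs.** From section 6.4: two-sided alpha 0.05, power 0.95, Delta 0.3, rho 0.9, 74 per group, 30% attrition. From the summary and section 8.1.1: d = 0.3. From section 10.1: a mixed model with baseline as covariate, which for the T4 difference behaves much like a baseline-adjusted comparison. Rho below 0.9 is my assumption; the protocol offers no other value.

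**1. Reproducing the protocol's figure.** Noncentral F test with 1 and 2n − 2 degrees of freedom and noncentrality 2n × Delta².
- n = 73: 146 × 0.09 = 13.14, power 0.9496.
- n = 74: 148 × 0.09 = 13.32, power 0.952.

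So 74 is the smallest n reaching 0.95. Then 74/0.7 = 105.7, rounded up to 106 per arm, 212 in total. Rho does not enter, because Delta is already divided by an error variance that contains it.

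**2. What Delta = 0.3 means in raw terms.** For the group-by-time effect with two equal arms, Delta = D / (2 × SD of change) and SD of change = SD × √(2(1 − rho)). Hence D = 0.6 × √(2(1 − rho)) in SD units. At rho 0.9, D = 0.6 × √0.2 = 0.27; at 0.5, D = 0.6 × √1 = 0.60. The last column of the table gives the rest.

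**3. Power for d = 0.3 with 74 completers per arm.** The noncentrality is:
- baseline-adjusted: 74 × 0.09 / (2(1 − rho²)); at rho 0.7 this is 6.66/1.02 = 6.53
- change score: 74 × 0.09 / (4(1 − rho)); at rho 0.7 this is 6.66/1.2 = 5.55

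| rho | Power, baseline-adjusted | Power, change score | Raw T4 difference equal to Delta = 0.3 (SD) |
|---|---|---|---|
| 0.9 | 99% | 98% | 0.27 |
| 0.8 | 86% | 82% | 0.38 |
| 0.7 | 72% | 65% | 0.46 |
| 0.6 | 62% | 53% | 0.54 |
| 0.5 | 55% | 44% | 0.60 |

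Solving for 95% power gives rho = 0.864 (baseline-adjusted) or 0.874 (change score). The difference detectable with 80% power, baseline-adjusted, is about (1.96 + 0.84) × √(2(1 − rho²)/74): 0.33 SD at rho 0.7 and 0.40 SD at 0.5.

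**4. How plausible 0.9 is.** The interval from T1 to T4 is 5 + 2 + 5 + 8.7 = 20.7 weeks, about 21. Under classical attenuation, with equal reliability on both occasions, the observed correlation is reliability times true-score correlation. The true-score correlation needed for 0.9 is therefore:
- reliability 0.92: 0.9/0.92 = 0.98
- reliability 0.90: 0.9/0.90 = 1.00
- reliability 0.88: 0.9/0.88 = 1.02

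Even at the top of the quoted range, participants' symptom ranking would have to stay almost fixed for five months of a treatment trial. Selecting on K10 above 15.9 (section 6.2) would tend to narrow the baseline range and lower rho further; I have not quantified that.

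**The case against.** The strongest defence is that section 6.4 is internally correct. It defines its 0.3 as Delta, and for that quantity 74 per group gives 95% power at any rho. This stands: a reader might infer that the 74 is wrong or that it was obtained from rho, and the arithmetic supports neither. In fact d = 0.3 with rho = 0.9 would need only 56 (baseline-adjusted) to 59 (change score) per group, so 74 cannot have come from that pair.

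It is also tempting to call 0.9 unattainable because it exceeds the scale's reliability. The protocol does not support that. The value lies inside the quoted 0.8 to 0.92, the quoted figures are internal consistency rather than test-retest reliability, and alpha can understate reliability. Nor does anything show that 0.9 was borrowed from the alpha values; the similarity is only suggestive.

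Finally, the size of the shortfall depends on a rho that I have assumed. That is true, but 95% power is already lost just below 0.87, so the conclusion does not need a pessimistic choice. Attrition below 30% would help: with all 106 per arm observed, baseline-adjusted power is about 95% at rho 0.8, 86% at 0.7 and 71% at 0.5.

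What the defence does not meet is that the protocol tells its readers, in two other places, that the 0.3 is a Cohen's d. That equation is roughly right only when rho is near 0.9.

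**Conclusion.** The point holds as a fault of an unsupported input joined to two effect-size definitions. It is not an arithmetic error. The 74 and the 212 are correct for Delta = 0.3. For the Cohen's d of 0.3 stated in the summary and section 8.1.1, 95% power with 74 completers per arm requires rho of at least about 0.864 to 0.874. The only value offered is an unsourced 0.9, implausibly high, though not impossible, over about 21 weeks with treatment in between. At an assumed rho of 0.5 to 0.7, power for d = 0.3 is 55% to 72% baseline-adjusted and 44% to 65% with change scores.

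These figures assume equal variances at both occasions, 74 completers per arm, and a T4 comparison that behaves like a baseline-adjusted or change-score analysis. Any gain from the intermediate visits or the further covariates in section 10.1 is not counted.

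**What to change.** Keep N = 212.

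1. Use one effect-size definition in section 6.4, section 8.1.1 and the summary. If it is Cohen's d, say which SD standardises it. Replacing rho alone would not be enough, since the 74 and its Delta-based 95% would not change.
2. Replace rho = 0.9 by a baseline-to-follow-up correlation with a source, for example from earlier PM+ trials, or show power for d = 0.3 over a range such as 0.5 to 0.8.
3. Replace the unconditional 95% for d = 0.3 by the resulting power, or by the detectable difference (with 80% power, baseline-adjusted, about 0.33 SD at rho 0.7 and 0.40 SD at 0.5).

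The cost is revised text in three places and a less favourable stated power. No extra participants are needed and the analysis does not change.
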